## **STUDY POPULATION AND TOTAL NUMBER OF SUBJECTS**

Patients of both sexes with advanced renal cell carcinoma will be included, who have received axitinib as second line or subsequent lines in accordance with the conditions approved for use in this disease.

The aim is to include two groups of patients: one with a long-term response to the drug (a group of patients progression-free for at least 9 months) compared to a group of patients who are refractory to the treatment (group of patients who show disease progression at the first assessment after the initiation of treatment).

The maximum possible number of patients will be included, progression-free at 9 months after the initiation of treatment. The ratio of long-term responders (PFS  $\geq$ 9 months) and primary refractory patients (PFS  $\leq$ 3 months) is estimated to be around 2:1.

During the study recruitment period, the participating sites may include all patients who meet the study’s inclusion criteria and who do not meet the study exclusion criteria. Given that this is an observational and exploratory study, no hypotheses have been established and the sample size will not be pre-determined.

In this study, the treatment with axitinib will have started before the enrolment of the patient, so the decision to treat and enrol these patients will be independent of the decision to carry out this study, and will depend exclusively on the clinical judgement of the responsible doctor.

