### **8.2. Scope**

The patient population eligible for this study includes any patient with advanced or metastatic kidney cancer who has been treated with axitinib for at least 9 months or who has had PD as the best response to this treatment.

The requirements for a patient’s inclusion are that:

1. These patients must have received axitinib as second-line treatment or later, in accordance with its Summary of Product Characteristics. Two groups presenting extreme responses to the drug will be compared: one group of patients showing no evidence of disease progression for at least 9 months after the start of treatment with axitinib versus a group of patients showing disease progression while taking the drug at the first response assessment.
2. Collection of clinical, safety and response data in patients with advanced kidney cancer.

The study is expected to be conducted in at least 30 sites distributed throughout Spain in order to reach the maximum number of study patients.

The study will start at each site after the contract with the site is signed and all study documentation and information on the procedures and objectives of the study are received by the person appointed by the sponsor.

Recruitment will be competitive between all participating sites, and as many patients as there are at the site that meet the inclusion criteria during the recruitment period may be included.

This is an observational study designed to reflect routine clinical practice; there will be no interference with the daily routine medical care of patients with kidney cancer. The data collected will be consistent with those normally collected from the patient’s medical record in routine clinical practice, including the patients’ demographic data, routine laboratory values required in the diagnosis and control of this condition, performance status, clinical condition, and the assessments carried out according to the site's routine clinical practice, use of medication, tolerability, adverse events and compliance with treatment.

Given that this is an observational study, no additional material not included in routine practice will be required.

Patients will be considered assessable if they meet the inclusion criteria and do not meet the exclusion criteria, and have received at least one dose of axitinib prior to their inclusion in the study.

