### **8.3. Variables**

For this observational study, the following variables will be recorded: demographic, medical history (including date and stage of disease at diagnosis and at progression), surgical treatment, histology, blood count and blood biochemistry, first-line treatments, associated adverse events, clinical efficacy and history of treatment with axitinib, including treatment line (second, third, etc.), dose, reason and date of start of treatment, disease risk criteria before onset, comorbidities, associated adverse events, concomitant medication and subsequent treatments, as well as the patient’s condition (alive, deceased) and the last date on which contact was made.

A complete description of the variables, including the operational definitions, will be detailed in the Statistical Analysis Plan of the study.

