### **8.5. Sample size**

Given the low incidence of metastatic renal cell cancer, and thus the population to be included in the study, the number of patients expected to be included will be small, and it is expected that it will be around 60 patients. However, as it is an observational and exploratory study, no hypotheses were specified and, therefore, the calculations of the sample size are not applicable.

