### **4 HYPOTHESIS AND DECISION RULES**

The level of significance will be  $\alpha=0.05$  two-tailed in all the statistical inference tests. Adjustment by multiple comparisons is not planned.

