          - Reason for starting this treatment (DP in the 1st line treatment/Toxicity in the 1st line treatment/Other, specify)
          - Start date
          - End date
          - Reason for treatment withdrawal (DP/Toxicity/Other, specify)
          - Has there been disease progression? (No/Yes, specify date)
          - Best treatment response (CR, PR, SD, DP/Not evaluable).
            - Date of the best response obtained
        - 3rd-line treatment
          - Drug
          - Starting dose
          - Reason for starting this treatment (DP in the 2nd line treatment/Toxicity in the 2nd line treatment/Other, specify)
          - Start date
          - End date
          - Reason for treatment withdrawal (DP/Toxicity/Other, specify)
          - Has there been disease progression? (No/Yes, specify date)

- 
- Best treatment response (CR, PR, SD, DP/Not evaluable).
    - Date of the best response obtained
  - Treatment with axitinib
    - Treatment line in which it was received.
    - Reason for starting treatment with axitinib (DP in previous treatment line/Toxicity in previous treatment line/Other, specify).
    - Risk criteria at the initiation of treatment with axitinib
      - Time from first diagnosis to systemic treatment less than 1 year (Yes/No/Unknown)
      - ECOG/PS (current status) (Yes/No/Unknown)
      - LDH >1.5 x ULN (Yes/No/Unknown)
      - Haemoglobin < LLN (Yes/No/Unknown)
      - Corrected calcium >10 mg/dl (Yes/No/Unknown)
      - Presence of 2 or more metastatic sites (Yes/No/Unknown)
      - Platelets > ULN (Yes/No/Unknown)
      - Neutrophils > ULN (Yes/No/Unknown) (value)
      - Lymphocytes (Yes/No/Unknown) (value)
      - Smoking habits (Smoker/Non-smoker/Former smoker)
    - Presence of comorbidities
      - Kidney failure (Yes/No)
        - If yes, specify, Creatinine Clearance (Mild, 60-89 ml/min/ Moderate, 30-59 ml/min/ Severe, 15-29 ml/min/ End Stage, <15 ml/min/ Dialysis)
      - Liver failure (Yes/No)
        - If yes, specify, Child Pugh (A/B/C)
      - Cardiovascular (Yes/No)
        - If yes, specify (multi-response question)
          - Decreased LVEF, specify %
          - Heart failure
          - Previous arrhythmia
          - Previous ischaemia
          - Controlled HTN, specify number of antihypertensive agents
          - Other, specify
      - Respiratory disease (Yes/No), specify
      - Other comorbidity (Yes/No), specify
    - Start date of treatment with axitinib

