  - Baseline LDH levels  $>1.5 \times \text{ULN}$  (yes vs no). At the beginning of 1st line
  - Baseline Hgb levels  $\leq \text{LLN}$  (yes vs no). At the beginning of 1st line
  - Baseline corrected Ca++ levels  $>10$  mg/dl (yes vs no). At the beginning of 1st line
  - Baseline neutrophil levels  $> \text{ULN}$  (yes vs no). At the beginning of 1st line
  - Baseline platelet levels  $> \text{ULN}$  (yes vs no). At the beginning of 1st line
  - Smoking habits (smoker, non-smoker or former smoker). At the beginning of 1st line
  - Baseline LDH levels  $>1.5 \times \text{ULN}$  (yes vs no). At the beginning of axitinib treatment
  - Baseline Hgb levels  $\leq \text{LLN}$  (yes vs no). At the beginning of axitinib treatment
  - Baseline corrected Ca++ levels  $>10$  mg/dl (yes vs no). At the beginning of axitinib treatment
  - Baseline neutrophil levels  $> \text{ULN}$  (yes vs no). At the beginning of axitinib treatment
  - Baseline platelet levels  $> \text{ULN}$  (yes vs no). At the beginning of axitinib treatment
  - Smoking habits (smoker, non-smoker or former smoker). At the beginning of axitinib treatment

A logistic regression model will then be carried out to study the association between belonging to each of the two extreme treatment response groups, with each of the possible clinical factors of interest, prior to axitinib treatment. That is, those baseline factors (prior to the start with axitinib) that have been studied in section 7 and that are significant ( $P < 0.05$ ) or close to significance ( $P < 0.15$ ).

The factors in this situation will be summarized below, and that potential prognostic factors of the response to axitinib treatment (long responding group vs refractory group) are considered.

---

The optimal model of prognostic factors will be constructed with the variables that are finally significant ( $P < 0.05$ ).

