Low Karnofsky performance status (< 80%), low serum hemoglobin, and high corrected calcium were identified as risk factors. Corrected calcium and hemoglobin were dichotomized using previously defined cut-points (corrected calcium, < 10 v ≥ 10 mg/dL; hemoglobin, ≤ 13 v > 13 g/dL for males and ≤ 11.5 v > 11.5 g/dL for females [45]), and the univariate association of these dichotomized variables with survival is given in the right side of Table 4. A multivariate Cox model was then fit using the categoric forms of the variables (Table 5). Each patient was then assigned to one of three risk groups: those with zero risk factors (**favorable risk**), those with one risk factor (**intermediate risk**), and those with two or three risk factors (**poor risk**).”

Parameter	Parameter Estimate	SE	$\chi^2$	P	Risk Ratio	95% CI
KPS	1.26	0.26	23.4	< .001	3.5	2.1 to 5.9
Corrected calcium	1.21	0.28	18.7	< .001	3.4	1.9 to 5.8
Hemoglobin	0.50	0.21	5.5	.02	1.7	1.1 to 2.5

  

No. of Risk Factors	No. of Patients* (%)	No. of Patients Alive	Median Survival (months)	95% CI	1-Year Survival	3-Year Survival
0	56 (42)	13	22.1	17.7 to 26.3	76%	25%
1	46 (35)	8	11.9	8.3 to 16.2	49%	11%
2 or 3	30 (23)	3	5.4	4.8 to 6.5	11%	0%

NOTE. Analysis performed for patients enrolled after 1/1/1990.  
 Abbreviation: KPS, Karnofsky performance status.  
 \*Five patients are missing data on one of the risk factors.

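### Four laboratory markers are recorded only as above/below-limit ticks and neutrophils are tested alone only as a cut; against a continuous test in about 60 patients this costs roughly 12 to 41 points of power, under assumed inputs

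*SAP*

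**What the plan says.** SAP section 6 states that it gives all the variables recorded in the CRF. Among the risk criteria at axitinib start, LDH is entered as "LDH >1.5 x ULN (Yes/No/Unknown". Haemoglobin (below LLN), corrected calcium (above 10 mg/dl) and platelets (above ULN) have the same form with no value field. Neutrophils have a tick and a value; lymphocytes also have a value.

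Protocol 8.2 speaks of "routine laboratory values required in the diagnosis and control of this condition", and Protocol 8.3 lists "blood count and blood biochemistry" among the recorded variables. Protocol 7.1 nevertheless defines LDH, haemoglobin, calcium, neutrophils and platelets as yes/no factors at a limit. SAP 7.1 follows it, for instance with "Baseline platelet levels" split at ULN.

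For the second-line MSKCC group, SAP section 7 uses haemoglobin below LLN and corrected calcium above 10 mg/dl. The source extract in SAP Appendix A1.3 uses other cuts: "corrected calcium, < 10 v ≥ 10 mg/dL; hemoglobin, ≤ 13 v > 13 g/dL for males", with 11.5 g/dL for females.

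**The concern.** To tick the box, a site must look up the result and then discard the number. Each marker is then a separate candidate in the primary association analysis, and the univariate P value (below 0.05, or below 0.15) decides whether it enters the logistic model. The published cuts are needed to build the risk groups. When a marker is examined on its own, splitting it at a limit discards information that a sample of about 60 can hardly spare, most of all when few patients lie beyond the limit. A relevant marker could then fail the screen for lack of power.

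A tick also fixes the cut-point at data entry. No other threshold can be applied later, and the risk groups cannot be checked against the underlying values.

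**Working it through.** **Inputs from the documents.** Sample size: "it is expected that it will be around 60 patients" (Protocol 8.5). The ratio of long-term responders to refractory patients "is estimated to be around 2:1" (Protocol synopsis), which gives 60 × 2/3 = 40 versus 60 × 1/3 = 20. Alpha is 0.05, "two-tailed in all the statistical inference tests" (SAP 4), with no multiplicity adjustment. Binary factors are tested by chi-squared, or Fisher's exact test when applicable (SAP 9.1); I take 'applicable' to mean an expected count below 5. The plan has no power figure to reproduce, because Protocol 8.5 declares a sample size calculation not applicable.

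**Assumed inputs (not in the documents).** The marker is normal (on the log scale if skewed) with equal SD, and shifted by d = 0.5 to 1.0 SD between groups. The overall adverse share is 10% to 50%.

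**Power on the value.** Two-sample t test with 58 df, critical value 2.002 and noncentrality d × √(40 × 20 / 60) = 3.651d. At d = 0.7 this is 2.556, giving 71.0%.

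**Power on the tick.** The cut c is placed so that (2/3)·P(Z > c) + (1/3)·P(Z > c − d) equals the overall adverse share. At d = 0.7 and 10%, the adverse shares are 5.6% and 18.8%; check: (40 × 0.056 + 20 × 0.188)/60 = 0.10. Exact enumeration of the two binomials under the SAP's test rule gives 32.7%.

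| d (SD) | Value | Tick, 10% adverse | Tick, 30% | Tick, 50% | Loss over 10–50% (points) |
|---|---|---|---|---|---|
| 0.5 | 43.5% | 18.8% | 28.4% | 31.6% | 12–25 |
| 0.6 | 57.7% | 25.3% | 38.4% | 42.3% | 15–32 |
| 0.7 | 71.0% | 32.7% | 49.3% | 53.5% | 17–38 |
| 0.8 | 81.9% | 40.7% | 60.2% | 64.5% | 17–41 |
| 1.0 | 94.8% | 56.7% | 79.0% | 82.5% | 12–38 |

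**The opposite case: a step at the limit.** Here only the adverse share differs between groups, and values on either side of the limit carry no further information (4,000 simulated trials each, 40 versus 20).

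| Adverse share, responders / refractory | Tick (Fisher) | Value (Mann–Whitney) |
|---|---|---|
| 20% / 50% | 62% | 48% |
| 10% / 40% | 71% | 47% |
| 30% / 65% | 69% | 60% |

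The tick is then the better coding.

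**Cut-points side by side.**
- Haemoglobin as a separate factor: the CRF tick is below LLN. SAP 7.1 uses at or below LLN, and Protocol 7.1 splits at above LLN. A patient exactly at LLN is ticked No on the CRF but belongs to the low group in both analysis definitions. The tick cannot resolve this.
- Second-line MSKCC, SAP section 7 version: haemoglobin below LLN and calcium above 10 mg/dl match the ticks, so both factors are available.
- Second-line MSKCC, published version (Appendix A1.3): the sex-specific haemoglobin cut cannot be recovered from a below-LLN tick. Calcium differs only at exactly 10.0 mg/dl.

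**The case against.** The strongest reply is that Protocol 7.1 pre-specifies these factors as binary, and the CRF collects what that analysis needs. That stands. No planned power is lost; the loss is measured against a continuous analysis that neither document plans for these markers. Continuous factors are not foreign to the plan, though: SAP 7.1 lists first-line duration and number of previous lines uncategorised as well as cut.

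A reader might infer that the CRF breaks a promise in Protocol 8.2 and 8.3. The wording there is too general for that. Section 8.2 describes data normally found in the medical record, and 8.3 names groups of variables and leaves operational definitions to the SAP.

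The CRF annex is not reproduced, and the SAP list may be abbreviated: ECOG/PS is also shown as Yes/No/Unknown although it is analysed as 0, 1 and 2 or more. If values were in fact recorded, only the SAP needs changing.

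Timing also counts. SAP version 3 (24 October 2019) was revised after draft results, and data collection was expected to end on 30 December 2018. Retrieving values now means reopening charts, and new codings would be chosen with results in view.

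**Conclusion.** The point holds as a method improvement of modest weight. Four markers (LDH, haemoglobin, corrected calcium, platelets) are tick-only as listed. For neutrophils the issue is analysis coding, not capture, so it would be wrong to say that all five lack values.

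The cut costs about 12 to 41 points of power if the marker shifts smoothly by 0.5 to 1.0 SD and 10% to 50% of patients are adverse. These are assumptions, and a pure step at the limit reverses the ranking.

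Two stronger readings should be resisted. One is that null results would be an artefact of the coding: at 0.5 to 0.6 SD even the value has only 44% to 58% power, so nulls are likely under either coding. The other is that the second-line MSKCC score cannot be built: the SAP's own version can, and among the published cuts only the haemoglobin one is out of reach, apart from calcium at exactly 10.0 mg/dl. The mismatch between below LLN and at or below LLN needs no assumption and should be corrected in any case.

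**What to change.** 1. In SAP 7.1, add the neutrophil count at axitinib start as a continuous factor. It is already recorded, so this needs no new data.
2. In the CRF variable list (SAP section 6, Protocol Annex 2), record the value, unit and site limit for LDH, haemoglobin, corrected calcium and platelets at axitinib start. Derive the ticks and risk groups centrally. Add one continuous coding per marker: LDH/ULN and platelets/ULN on the log scale, haemoglobin relative to LLN or adjusted for sex, and corrected calcium as measured. Keep the protocol's binary factors as specified.
3. Use one haemoglobin cut in the CRF list, Protocol 7.1 and SAP 7.1.
4. Label any continuous analysis added now as post hoc, because SAP version 3 followed draft results. If the values cannot be retrieved, report null results for the four tick-only markers as low-powered.

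The cost is SAP wording for items 1, 3 and 4. Item 2 needs a chart query for about 60 patients across the participating sites (at least 30 planned), with four numbers and their limits per patient. The statistical downside is lower efficiency of a linear term if a marker's effect is a true threshold; keeping the binary factors alongside covers that case.

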## 7 DEFINITION OF VARIABLES AND OBJECTIVES

In addition, the following variables will be calculated from the CRF data:

NOTE: In patients with dates after the date of the IC visit / signature, the date of the IC visit / signature has been considered as the date of the last check. Due to the retrospective nature of the study, no data can be collected after the patient was included in the IC study / signature.

- Age (years) of patient at time of visit= (Visit date – Date of birth) / 365.25
- Age (years) at first diagnosis= (Date of first diagnosis – Date of birth) / 365.25
- Age (years) at the initiation of axitinib= (start date of axitinib – Date of birth) / 365.25
- Number of metastatic locations = sum (Lymph nodes, CNS, Hepatic, Pulmonary, Bone, Other).
- • Neutrophil / lymphocyte ratio. It will be categorized as follows:  $\leq 3$ ,  $> 3$ . "Before the beginning of the first line" and "At the beginning of treatment with axitinib" will be analyzed. This ratio is not calculated on axitinib suspension because there is no current lymphocyte value data in that part of the CRF.
- Time (months) between first diagnosis and nephrectomy = (Date of nephrectomy – Date of first diagnosis) / 30.4375. A list with the information (site, patient, date of first diagnosis, date of nephrectomy and the calculated time) in cases in which the time is negative (with date of nephrectomy before or equal to date of first diagnosis) will be displayed, and these cases will not be included in the descriptive analysis
- Time (months) between first diagnosis and radiotherapy = (Date of radiotherapy – Date of first diagnosis) / 30.4375. A list with the information (site, patient, date of first diagnosis, date of radiotherapy and the calculated time) in cases in which the time is negative (with date of radiotherapy before or equal to date of first diagnosis) will be displayed, and these cases will not be included in the descriptive analysis.
- Time (months) between first diagnosis and 1st-line treatment = (Date of the initiation of 1st-line treatment – Date of first diagnosis) / 30.4375. A list with the information (site, patient, date of first diagnosis, date of 1st-line treatment and the calculated time) in cases in which the time is negative (with date of 1st-line treatment before or equal to date of first diagnosis) will be displayed, and these cases will not be included in the descriptive analysis
- Duration (months) of previous 1st-line treatment = (Date of end of 1st-line treatment – Date of start of 1st-line treatment) / 30.4375. If a patient is detected in whom this duration cannot be calculated or a negative time is left, it will not be considered in the descriptive analysis, and a list will be shown with the information related to this calculation of said patient.

- 
- Pre-treatment of 1st line: a descriptive table with the collected drugs will be shown (if necessary, a list will be sent to the sponsor for the grouping of these drugs). In addition, the registered drugs will be grouped into three groups: Sunitinib, Other iTK, and Others, and the descriptive table will be included in the report.
  - Duration (months) of previous 2nd-line treatment =  
 $(\text{Date of end of 2nd-line treatment} - \text{Date of start of 2nd-line treatment}) / 30.4375$ . If a patient is detected in whom this duration cannot be calculated or a negative time is left, it will not be considered in the descriptive analysis, and a list will be shown with the information related to this calculation of said patient.
  - Duration (months) of previous 3rd-line treatment =  
 $(\text{Date of end of 3rd-line treatment} - \text{Date of start of 3rd-line treatment}) / 30.4375$ . If a patient is detected in whom this duration cannot be calculated or a negative time is left, it will not be considered in the descriptive analysis, and a list will be shown with the information related to this calculation of said patient.
  - Duration (months) of previous 4th-line treatment =  
 $(\text{Date of end of 4th-line treatment} - \text{Date of start of 4th-line treatment}) / 30.4375$ . If a patient is detected in whom this duration cannot be calculated or a negative time is left, it will not be considered in the descriptive analysis, and a list will be shown with the information related to this calculation of said patient.
  - Duration (months) of previous 5th-line treatment or further =  $(\text{Date of end of 5th-line treatment} - \text{Date of start of 5th-line treatment}) / 30.4375$ . It will be analyzed only if there is an adequate sample (enough high) of patients with 5th or later previous lines.
  - Duration (months) of treatment with axitinib =  
 $(\text{Date of end of axitinib treatment or of latest follow-up if not suspended} - \text{Date of start of axitinib treatment}) / 30.4375$
  - Time (months) to increase or Time (months) to reduction of axitinib dose =  
 $(\text{Dose increase date or Dose reduction date} - \text{Start date of treatment with axitinib}) / 30.4375$
  - Duration (months) of subsequent treatments =  
 $(\text{Date of end of subsequent treatment or of latest follow-up if not suspended} - \text{Date of start of subsequent treatment}) / 30.4375$ . In the case of several subsequent treatments per patient, proceed as follows: the duration in months of each of the subsequent treatments will be calculated (from the start date to the end date or last check if it continues). This will be done for all subsequent treatments and then proceed to make the sum per patient of all durations of subsequent treatments

- Progression-Free Survival (PFS, in months) =  
 (Date of Disease Progression on treatment with axitinib or death from any cause – Date of start of treatment with axitinib) / 30.4375  
 If there is no progression or death, the case is censored as  
 PFS (months) = (Date of latest follow-up – Date of start of treatment with axitinib) / 30.4375
- Time to progression (TTP, in months) =  
 (Date of Disease Progression – Date of start of treatment with axitinib) / 30.4375  
 If there is no progression, the case is censored as  
 TTP (months) = (Date of latest follow-up – Date of start of treatment with axitinib) / 30.4375
- Overall Survival (OS, in months) = (Date of death – Date of start of treatment with axitinib) / 30.4375  
 If death has not occurred, the case is censored as  
 Overall Survival (OS, in months) = (Date of latest follow-up – Date of start of treatment with axitinib) / 30.4375
- Overall Survival since the start of first-line treatment (OS, in months) = (Date of death – Date of start of first-line treatment) / 30.4375  
 If death has not occurred, the case is censored as  
 Overall Survival (OS, in months) = (Date of latest follow-up – Start date of first treatment) / 30.4375
- Patient subgroups
  - A-Long-term responders: comprising patients with PFS  $\geq 9$  months.
  - B-Refractory (primary): comprising patients with best response to treatment = PD. This date is collected in the CRF form “axitinib treatment”.
- MSKCC risk group (described in appendix 11.1.). It will be analysed “Before the beginning of the first line”. These calculations will be performed on patients who have data on all the variables involved (in the case of a patient who does not have data on all the variables but has > 2 factors, it will be classified in the “Poor” risk group.

Risk groups are defined considering the following five factors (Favourable, Intermediate, Poor):

- ECOG/PS <1 (related to KPS <80)
- Time from first Diagnosis to Systemic Treatment less than 1 year
- LDH >1.5 x ULN
- Corrected calcium >10 mg/dl
- Haemoglobin < LLN

---

The risk groups are as follows:

- Favourable: 0 factors
  - Intermediate: 1 or 2 factors
  - Poor: >2 factors
- 
- Heng (or IMDC) risk group (described in appendix 11.1.). It will be analysed “at the beginning of the axitinib treatment” and “on the axitinib discontinuation”. These calculations will be performed on patients who have data on all the variables involved (in the case of a patient who does not have data on all the variables but has > 2 factors, it will be classified in the “Poor” risk group.

Risk groups are defined taking into account the following six factors (Low, Intermediate, High):

- ECOG/PS <1 (related to KPS <80)
- Time from first Diagnosis to Systemic Treatment less than 1 year
- Corrected calcium >10 mg/dl
- Haemoglobin < LLN
- Neutrophils > ULN
- Platelets > ULN

The risk groups are as follows:

- Favourable: 0 factors
  - Intermediate: 1 or 2 factors
  - Poor: >2 factors
- 
- Risk group according to MSKCC Criteria for patients previously treated with a TKI (defined in appendix 11.1). It will be analysed “at the beginning of the axitinib treatment”. Of note, all patients must have been previously treated with a TKI. These calculations will be performed on patients who have data on all the variables involved (in the case of a patient who does not have data on all the variables but has > 2 factors, it will be classified in the “Poor” risk group.

Risk groups are defined taking into account the following three factors (Low, Intermediate, High):

- ECOG/PS <1 (related to KPS <80)
- Haemoglobin < LLN
- Corrected calcium >10 mg/dl

The risk groups are as follows:

- Favourable: 0 factors
- Intermediate: 1 factor
- Poor: 2 or 3 factors
- The Objective Response Rate (ORR) is the frequency of subjects with CR or PR.
- The Clinical Benefit Rate is the frequency of subjects with CR, PR or SD.
- Increase of the axitinib dose to above 5 mg twice daily. Defined as having specified "Increase" at least one time, and in this case having specified "New dose" >5 mg/12h.
- Reduction of the axitinib dose to below 5 mg twice daily. Defined as having specified "Reduction" at least one time, and in this case having specified "New dose" <5 mg/12h.

